### 7.1.1 PRenancy outcome Intensive Monitoring (PRIM)

PRIM is a non-interventional data collection process based on pharmacovigilance and does not impose a treatment, diagnostic/ therapeutic procedure, or a clinical visit schedule.

Whenever possible (based on the consent of the reporter to provide further information and availability of contact details), cases will be followed and processed following the PRIM principle.

The following cases are considered not applicable for the PRIM monitoring process since they do not allow for further follow-ups/contacts:

- Patients who upon initial report refuse to be contacted to obtain or provide FU information;
- Indirect cases (e.g. reported by someone other than the patient or the HCP) for which the reporter refuses to provide FU information;
- Cases lacking reporter contact details (e.g. cases from social media) or incomplete cases (i.e., missing  $\geq 1$  of 4 elements: identifiable patient, identifiable reporter, a suspect drug, and an adverse event or adverse drug reaction);
- Cases where reporter mentions in the initial report that he/she does not have more information and will not have more in the future.

A specific set of targeted FU checklists will enable the collection of all necessary information to evaluate safety data on Kesimpta exposure and associated pregnancy, fetal and infant outcomes. Development, approval and distribution of these targeted FU checklists will follow the applicable SOP.

Targeted FU Checklists collect the minimum information necessary, which include the core data points required for analysis.

Cases are followed up as per the schedule in [Table 7-1](#), using targeted FU checklists.

**Table 7-1 Follow-up schedule using targeted FU checklists\***

| FU number | Checklist name                                   | Date of collection  | Type of information collected                        |
|------------------|---|--|---|
| FU 1             | Pregnancy Checklist - Baseline                          | As soon as possible after initial report, or at initial report if possible | Baseline characteristics and demographics of the mother     |
| FU 2             | Pregnancy Checklist – Pregnancy Outcome                 | Between EDD and EDD+30 days  | Information related to the delivery and neonate details     |
| FU 3             | Pregnancy Checklist – Infant Health Status at 3 months  | EDD + 3 months   | Information related to infant health status and development |
| FU 4             | Pregnancy Checklist – Infant Health Status at 6 months  | EDD + 6 months   | Information related to infant health status and development |
| FU 5             | Pregnancy Checklist – Infant Health Status at 12 months | EDD + 12 months  | Information related to infant health status and development |

\* FU schedule and requirements to be included in Kesimpta pharmacovigilance guidance document (PGD).

EDD – estimated date of delivery

### **7.1.2 Adjudication process**

The individual case safety report (ICSR) of with reported potential congenital anomaly, i.e. each individual case of reported congenital abnormality or other outcome (spontaneous abortion, elective termination or stillbirth) for which there is evidence of a birth defect, will undergo adjudication. These cases will be identified from the Novartis global safety database as cases with an AE with seriousness classification “congenital anomaly” and with fetal outcome coded as “congenital anomaly major”, “congenital anomaly minor” and “congenital anomaly NOS (structural)”.

The adjudication panel will consist of three independent external experts in the field of teratology or reproductive toxicology. Two of the three experts will perform the initial independent adjudication of individual case. The third expert will be contacted in case of different opinions by the two initial adjudicators.

Adjudicators will evaluate the data to determine whether the malformation was major, minor and/or of chromosomal origin using European Surveillance of Congenital Anomalies (EUROCAT) and Metropolitan of Atlanta Congenital Defects Program (MACDP) classification criteria.

The outcome per EUROCAT classification will be considered as the main classification entered in the Novartis global safety database accordingly. The MACDP classification will be kept in the notes. Reports with insufficient information for adjudication will be classified as “congenital anomaly not otherwise specified (NOS)”.

The full adjudication process, role and responsibilities and data handling will be described in a separate adjudication charter.

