**Table 7-3 Pregnancy outcome follow-up checklist variables**

| Variable                              | Data captured   |
|---------------------------------------|---|
| Medications taken by the mother       | Name, dose, route of administration, start/stop, trimester of exposure  |
| Prenatal test                         | Name, date, abnormal (Yes/No/Not available), result (free text)   |
| Pregnancy outcome                     |   |
| Live birth                            | Date of birth, Gestation weeks at birth
Timing: full-term vs. premature vs. post mature
Normal (yes/no)
Neonate demographics (at birth):
Gender, weight (kg/lb and percentile),
Length (cm/in and percentile),
Head circumference (cm/in and percentile)
Small for gestational age*** (Yes/No)
Apgar Score 1min, 5min and 10 min
Infant status (alive/deceased)
Date of death
Cause of death |
| Termination                           | Date, Gestation weeks
Type: spontaneous abortion/miscarriage vs. induced termination
(therapeutic reason vs. elective termination)
Medical problem: Blighted ovum, molar pregnancy, ectopic pregnancy, Other
(free text)  |
| Stillbirth                            | Date, Gestation weeks
Autopsy (Yes/No/Unknown), free text  |
| Anomalies in the baby or fetus        | Anomaly notes (yes/no/unknow)
Description (free text)
Anomaly of known origin (No/Yes specify)
If least one major anomaly (Yes/ No only minor/ None /Unknown)  |
| Complication during or after delivery | None vs. Intrauterine death vs. Other specify   |

\*\*\* Yes, if the birth weight is <10th percentile for the GA ([Battaglia and Lubchenco 1967](#))

Low birth weight will be derived based on the weight at birth. If the weight is <2500g (i.e. 5 pound and 8 ounces) this will be considered low ([Cutland C et.al., 2017](#)).

Pregnancy and fetal/infant outcomes that are defined according to Manual of Argus Processing (MAP) are listed in [Table 7-4](#) and [Table 7-5](#). These will be used in the tabulations and analyses of primary or secondary outcomes.

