**Table 7-5 Definition of key fetal/infant outcomes**

| Fetal outcome Argus terminology                | Definition  |
|--|---|
| Normal baby/normal infant                      | Live birth where there is no mention of fetal abnormalities or perinatal complications (regardless of gestational age at birth).  |
| Congenital anomaly major*                      | A congenital abnormality that requires medical or surgical treatment, has a serious adverse effect on health and development, or has significant cosmetic impact.             |
| Congenital anomaly minor**                     | A congenital abnormality that does not require medical or surgical treatment, does not seriously affect health and development, and does not have significant cosmetic impact |
| Congenital/other (structural) abnormality, NOS | Reported congenital anomaly without diagnostic information or other structural anomalies not well described.  |
| Perinatal complication (nonstructural)         | Non-structural perinatal complication of fetus: from 22 weeks of gestation (154 days) to 7 days after birth.  |
| Post-perinatal complication (nonstructural)    | Non-structural post-perinatal complications of fetus: following 7 days after birth.   |
| Abnormality, other (nonstructural)             | Non-structural abnormalities not related to delivery, other non-structural anomalies not well described or anomalies reported as normal variant                               |

| Fetal outcome
Argus terminology | Definition   |
|--|---|
| Fetal death / intrauterine death           | Fetal death confirmed by pre-natal tests, followed by a spontaneous abortion or requiring a therapeutic abortion, or stillbirth.                |
| Blighted ovum                              | Absence of an embryo in a normal-appearing gestational sac visible on ultrasound.   |
| Ectopic pregnancy                          | Implantation of the embryo outside the uterine cavity   |
| Hydatidiform mole                          | Gestational trophoblastic disease where a non-viable fertilized egg or embryo implants in the utero and grows into a mass (instead of a fetus). |
| Infant status unknown                      | Information regarding the infant is not known   |
| Outcome pending                            | The outcome of the fetus/infant is not known (queries are pending or due date is in the future)   |

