| Lost to follow up                          | No further information is received regarding pregnancy outcome even after pursuing appropriate number of follow-ups for a case                  |

\*To be used in the analysis of the primary outcome

\*\* To be used in the analysis of the secondary outcomes

Source: Manual for Argus processing - MAP chapter 13 Pregnancy cases, version 10.2, effective 15Jul2021

Table 7-6 lists variables collected via the Infant health status follow-up during first year of life FU checklists that will be used in the evaluation of secondary outcomes if sufficient data is reported.

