### 7.7.1 Analysis of primary and secondary endpoints

Analysis of the Kesimpta-PRIM data will include estimation of proportion (and 95% confidence interval) of malformations (major [primary endpoint], minor [secondary endpoint], and overall), and of specific pregnancy outcomes such as, spontaneous abortions, stillbirths and elective terminations. The proportion of congenital malformations will be calculated amongst: (1) live births; and (2) live births, stillbirths and TOPFA (termination of pregnancy for fetal anomaly). Proportion will be estimated overall and by pre-specified timing of drug exposure in pregnancy (as defined in [Section 7.3.1](#)).

In addition, major congenital malformations will also be summarized by SOC based on latest available MedDRA classification.

Minor congenital malformations will be listed by preferred term based on latest available MedDRA classification.

The proportion of **other adverse birth outcomes** associated with exposure to Kesimpta during pregnancy including preterm births, low birth weight and small for gestational age (SGA) will be estimated among live births.

The proportion of adverse effects with particular focus on serious infections in the infant during the first 12 months after birth will be provided.

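### Chromosomal origin is adjudicated, but the primary endpoint does not use it and the scope of the background rates is not stated

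*Protocol*

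**What the plan says.** Section 7.1.2 gives an external panel the task of classifying each reported anomaly: "Adjudicators will evaluate the data to determine whether the malformation was major, minor and/or of chromosomal origin". It then says: "The outcome per EUROCAT classification will be considered as the main classification entered in the Novartis global safety database accordingly". Cases reach the panel through three fetal-outcome codes: major, minor and not otherwise specified (structural). Section 7.4 says that malformation information is entered as described in Tables 7-4 and 7-5, from the reported verbatim and the adjudication.

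Table 7-5 has no chromosomal category. It defines the major code as "A congenital abnormality that requires medical or surgical treatment, has a serious adverse effect on health and development, or has significant cosmetic impact", and a footnote marks that code "To be used in the analysis of the primary outcome". The follow-up checklist in Table 7-3 also asks for "Anomaly of known origin".

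Section 7.7.1 plans "estimation of proportion (and 95% confidence interval) of malformations (major [primary endpoint], minor [secondary endpoint], and overall", in live births and in live births, stillbirths and TOPFA. It does not split these by origin.

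Section 7.7 plans a comparison with external background data for the primary cohort. Section 7.5 quotes 3% (US) and 2.6% (Europe) of live births without saying whether chromosomal anomalies are included. It also quotes a worldwide figure of about 6% that is expressly described by genetic or partly genetic origin. Table 7-8 uses 2%, 3% and 6% as background values.

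**The concern.** The panel makes a decision on origin that neither the primary outcome variable nor the planned estimates call for. Because the major code rests on severity alone, a chromosomal anomaly that needs treatment or seriously affects health meets the definition and counts.

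Two consequences follow. First, if exposure raises only non-chromosomal defects, the chromosomal cases add background events to the numerator and shrink the visible ratio. Second, the proportion is to be set beside external rates of unstated scope. If the cohort counts chromosomal cases and the reference does not, or the reverse, the comparison is biased whatever the drug does. The second consequence can be the larger, and without the panel's decision as an analysis variable the two sides are hard to align.

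**Working it through.** **Inputs from the protocol (Section 7.5, Table 7-8).** n = 500 live births; background p0 = 0.03 (alternative 0.026); exposed p1 = 0.06; exact two-sided one-sample binomial test, alpha 0.05.

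**Reproducing the stated power.** With at most 0.025 in each tail, X ~ Bin(500, 0.03) gives rejection at X ≤ 7 or X ≥ 24, with actual alpha 0.0347 (upper tail 0.0179). Power = P(X ≤ 7) + P(X ≥ 24) at p = 0.06 is 0.8926, the figure in Table 7-8. All nine rows of that table reproduce to four decimals.

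**Assumption.** The protocol gives no chromosomal share s of major malformations, so s = 10% to 30% is assumed, the same in cohort and background. Exposure is taken to double non-chromosomal defects only.

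- Pooled: p0 = 0.03; p1 = 0.03s + 2 × 0.03(1 − s); visible ratio = 2 − s.
- Removed from both sides: p0 = 0.03(1 − s); p1 = 2 × 0.03(1 − s); ratio 2.

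For s = 0.15, pooled p1 = 0.0045 + 0.0510 = 0.0555, ratio 1.85. With removal, p0 = 0.0255 and p1 = 0.0510.

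| Share s | Pooled p1 | Visible ratio | Power, pooled | Power, removed from both | Gain (points) |
|---|---|---|---|---|---|
| 10% | 0.0570 | 1.90 | 0.832 | 0.863 | 3 |
| 15% | 0.0555 | 1.85 | 0.794 | 0.846 | 5 |
| 20% | 0.0540 | 1.80 | 0.751 | 0.826 | 8 |
| 30% | 0.0510 | 1.70 | 0.648 | 0.779 | 13 |

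The fair comparison is between the two power columns. At s = 10%, power drops from 0.893 to 0.832. The part from 0.893 to 0.863 comes from having fewer events that exposure can double, and removal does not recover it.

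**At the 2.6% background**, same formulas:

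| Share s | Power, pooled | Power, removed from both |
|---|---|---|
| 5% | 0.839 | 0.805 |
| 10% | 0.805 | 0.793 |
| 15% | 0.767 | 0.780 |
| 20% | 0.724 | 0.765 |

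At 5% and 10% removal loses power. The exact test is discrete: at p0 = 0.026 its actual alpha is 0.048, and at p0 = 0.0247 the upper limit is still 21 events while actual alpha falls to 0.030.

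**Mismatched scope, total background 3%.**

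- All-anomaly cohort against a non-chromosomal background, no drug effect. The upper limit is set at p0 = 0.03(1 − s), while the true rate is 0.03. At s = 10, 15, 20 and 30% the limit is 22, 21, 20 and 18 events, and it is reached in 5.0%, 8.0%, 12.1% and 24.9% of studies. With matched all-anomaly scope the figure is 1.8%.
- Non-chromosomal cohort against an all-anomaly 3% background, true doubling. Power is 0.751, 0.648, 0.529 and 0.403 at s = 10, 15, 20 and 25%, below the pooled version at each share tabulated for both.

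**The case against.** The protocol does not say outright that chromosomal cases are included, and it defers detail. Adjudication data handling goes to a charter, the full list of analysis variables to the SAP and database conventions to a product guidance document. A tabulation with and without chromosomal cases could appear in any of these. That limits how firmly the omission can be put. It does not remove the point, because the protocol itself fixes the primary outcome variable and its definition, and neither uses origin.

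The study is also descriptive. The ENCePP checklist in Annex 2 says that no hypotheses are tested and no measures of association are given, and Section 7.9 cautions on external comparison. That stands, and it makes power only a yardstick for lost sensitivity. Section 7.7 nevertheless plans the background comparison, and scope matters to a descriptive comparison too.

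The share is unknown. Table 7-2 classes cases with abnormal prenatal results known at entry as retrospective, which takes some chromosomal cases out of the primary cohort. This too stands: the share may be small, and it may differ between cohort and background.

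A reader might infer four stronger things that the documents do not support:

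- **Exposure cannot cause chromosomal anomalies.** The protocol nowhere says so, and the exposure window opens 180 days before LMP, before conception.
- **The database cannot identify such cases.** Events are MedDRA-coded and the EUROCAT outcome is entered, so a reported chromosomal diagnosis could carry a coded term. What is missing is a named field for the panel's own decision.
- **The 89% power is wrong.** It is defined on total prevalence, 3% against 6%, and is correct.
- **Pooling causes the whole fall from 0.893.** Only part of it is recoverable, as the tables show.

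**Conclusion.** The point holds in this form: origin is adjudicated but plays no part in the primary outcome variable or the planned estimates, and the scope of the 3% and 2.6% backgrounds is unstated. On the protocol's definitions a severe chromosomal anomaly is a primary event.

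The recoverable power is about 3 to 13 points at a 3% background for assumed shares of 10% to 30%, and nothing at a 2.6% background for shares of 5% to 10%. The risk from mismatched scope is as large or larger: a false upper signal in about 5% to 25% of studies over the same 10% to 30% range. All of this rests on an assumed share, equal in cohort and background, and on an effect limited to non-chromosomal defects. The case for reporting both versions needs none of these assumptions. The evidence does not support making the non-chromosomal version decisive, since that trades fewer events against less dilution.

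**What to change.** - In Section 7.1.2 or 7.4, state that the panel's decision on chromosomal origin is kept in a field that the programmed analysis can retrieve.
- In Section 7.7.1, state that chromosomal cases count in the all-major estimate. Report the major malformation proportion with its exact confidence interval in both denominators, once for all major anomalies and once excluding those adjudicated as chromosomal.
- In Section 7.5, state whether each background figure includes chromosomal anomalies, and compare each version only with a background of the same scope. If no such background is available, give the estimate without a comparison.

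Which version carries more weight can remain the sponsor's reasoned choice. The cost is one field for a decision the panel already makes, extra table rows, and fewer events in the non-chromosomal version.

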## **7.2 Setting and study population**

The primary analysis cohort of interest will be the prospectively-reported pregnancies associated with maternal exposure during pregnancy or up to 180 days before LMP.

Retrospective pregnancy cases are defined as pregnancy cases with known pregnancy outcome [i.e. pregnancy outcome (live birth, stillbirth, spontaneous abortion, induced termination)] or known abnormal findings obtained from a prenatal test at the time of initial reporting to Novartis. Considering the high risk of bias resulting from retrospective reports, retrospective pregnancy cases will be processed, analyzed and presented separately from prospective cases. All necessary follow-up information will be presented for those retrospective cases.

Pregnancies with Kesimpta exposure prior to 180 days before LMP or exposure via father will be considered as Kesimpta unexposed cases, but will be processed and presented in a manner similar to the retrospective cases.

[Table 7-2](#) provides details on the prospective vs. retrospective case classification for Kesimpta-PRIM.

**Table 7-2 Kesimpta-PRIM prospective and retrospective case classificationa**

| Timing and results of prenatal testing   | Kesimpta PRIM case classification |
|---|--|
| Pregnancy outcome has not occurred, and prenatal tests have not been performed at the time of reporting or entry b     | Prospective                              |
| Prenatal testing was performed at the time of entry b , results have not been received by provider/patient/Novartis    | Prospective                              |
| Prenatal test results were available, and were known to be normal or results were not specified at the time of entry b | Prospective                              |
| Prenatal test results were available and were known to be abnormal at the time of entry b                              | Retrospective                            |
| Outcome of pregnancy known at the time of entry b  | Retrospective                            |

a) Definitions of retrospective and prospective cases as per EMA guidance

b) 'Entry' is considered the date of initial report received by Novartis for this case

### 7.2.1 Inclusion criteria – Kesimpta-PRIM study

All pregnancy cases with exposure to Kesimpta for MS and reported to Novartis global safety database via clinical trials, spontaneous post-marketing report sources, post-marketing observational studies, and patient-oriented programs are eligible for inclusion in the Kesimpta PRIM study.

### 7.2.2 Exclusion criteria – Kesimpta-PRIM study

Pregnancy cases identified via pregnancy registry study (OMBG157G2403) and cases reported to Novartis for non-MS indications will be excluded from Kesimpta PRIM study.

## 7.3 Variables

Key exposure, outcome and potential confounding variables are defined in [Section 7.3.1](#), [Section 7.3.2](#) and [Section 7.3.3](#) respectively.

Information provided in the initial report along with data collected using target follow up (FU) checklists will be considered. The target FU checklists will mainly focus on maternal information and include questions about pregnancy history, history of onset and other characteristics of disease, and current medication use. The FU checklists also captured data on other variables such as demographics, gestational age, co-morbidities, concomitant medications, disease severity and duration, and other relevant potential confounders. Exposure data will be collected at enrollment, between expected date of delivery (EDD) and EDD + 30 days, EDD + 3 months, EDD + 6 months and EDD + 12 months.

### 7.3.1 Exposure

Trimesters will be defined, based on the dose administered, as follows:

- “Peri-LMP”: LMP- 180 days to LMP,
- “1st trimester”: LMP to LMP+84 days,
- “2nd trimester”: LMP+85 days to LMP+182 days,
- “3rd trimester”: LMP+183 days and beyond.

Cases will be classified by timing of Kesimpta exposure i.e. as “Overall” vs. “Peri-LMP only” vs. “At least 1st trimester” vs. “Only after 1st trimester”.

### 7.3.2 Outcomes

Table 7-3 lists the variables collected via the Pregnancy Outcome FU checklists. These will be mapped, to the extent possible, to the Pregnancy and fetal/infant outcomes defined according to the Manual of Argus Processing (MAP) as described in Table 7-4 and Table 7-5. Note that some variables are kept as part of the narrative i.e. entered only as free text.

